6.4 SUBJECT COMPLETION AND WITHDRAWAL

SUBJECT COMPLETION

- A subject whose study ulcer has closed will be considered as having completed the study.
- A subject who completes the Treatment Phase will be considered as having completed the study.

SUBJECT PREMATURE WITHDRAWAL FROM THE STUDY

A subject who is randomized into the Treatment Period of the study but who does not complete the study through TV4 has prematurely discontinued.

All subjects have the right to withdraw at any point during treatment without prejudice. It will be documented whether or not each subject completed the clinical study. If for any subject, study treatment or observations were discontinued, the reason(s) will be recorded.

The Investigator can discontinue a subject at any time if it is considered medically necessary.

In addition, subjects WILL be withdrawn from the study, in consultation with the Medical Monitor and the Investigator, if any of the following are met:

- A subject is significantly non-compliant with the requirements of the protocol.
- A subject becomes pregnant (Note: the pregnancy will be followed up to term for safety follow-up. Relevant safety information collected after the study has completed will be reported as supplemental information.)
- A subject has revascularization surgery on the leg with the study (target) ulcer.
- A subject has a target ulcer wound bed that has exposed bone, tendon or fascia.
- The subject's study ulcer cannot be dressed with multi-layer compression.
- Two separate infections with no response to allowable treatments
- The subject's ulcer merges with an adjacent ulcer.

Premature withdrawal from the study MAY occur if:

- A subject is treated with a prohibited medication. This decision will be made by the Medical Monitor in conjunction with the Investigator as to whether premature withdrawal is warranted.

Every attempt should be made to collect follow-up information. The reason for treatment discontinuation or withdrawal from the study will be recorded in the source documents and on the appropriate page of the CRF.

Before a subject is identified as lost-to-follow up, the site should make all reasonable efforts to contact the subject. These attempts must be documented and should include at a minimum one phone call and one certified letter.

In the event that a subject is prematurely discontinued from the study at any time due to an adverse event of SAE, SAE procedures must be followed.

SCREEN FAILURES

A subject who has signed a consent form, has been assigned a screening number, but is not randomized is classified as a screen failure. Subject number, demography, and reason for screen failure will be collected.

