9.7 STATISTICAL METHODS

MISSING DATA

Missing data may be the result of missed visits, subjects lost to follow-up or who have died, or data not available (e.g., smoking status).

Missing primary endpoint data within 12 weeks from start of study will not be imputed for ITT populations as these will constitute right-censored data in the time to heal analysis. The last visit for which data are available will constitute the start of censoring (healing outcome). For secondary endpoints within 12 weeks from start of study, the last observation carried forward (LOCF) principle will be used for ITT populations.

For adjusted analyses of primary and secondary endpoints, missing data for covariates used to adjust analyses may be imputed in separate models when the missing data for each covariate is $\leq 30\%$ and it can be reasonably demonstrated that the missing data for each covariate are MCAR.

FINAL ANALYSIS

Analysis can be started when database lock for the trial is initiated. In regard to statistical modeling, the initial list of independent variables will be examined for correlation between pairs. In the event that

correlation (however calculated) exceeds 0.7, a selection will be made between the 2 variables to avoid possible issues of co linearity and variance inflation.

The following analysis will be conducted:

1. Flow chart (subjects)
2. Overall trial statistics (enrollment dates, site numbers, numbers of subjects)
3. Demographics between groups at baseline (no statistical testing but identification of likely trial imbalances)
4. Count of subjects in each group
5. Primary endpoints within 6 and 12 weeks (time to heal; previously defined by groups) will be analyzed by Kaplan-Meier and log rank test (unadjusted); and then Cox regression to adjust for the following variables (with and without covariate imputation):

- Site
- Year enrolled (if trial lasts 2 years or more)
- Treatment group
- Initial area at randomization (cm²)
- Initial wound depth (cm)
- Age of wound at enrollment (days)
- Smoking status
- Prior VLU
- Pain score at randomization
- Patient age
- Gender
- Ethnicity/race
- VCS score
- Diabetes
- Patient on pain medications
- Smoking status
- BMI
- Infection episodes

6. Secondary endpoints will be analyzed as follows:

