13.3 REPORTING PROTOCOL DEVIATIONS

The Investigator is obligated to follow the protocol without departure from the requirements written in the protocol. If the Investigator deviates from the protocol requirements, the Sponsor will make the determination as to whether the subject will continue in the study. The Sponsor also has the right to discontinue the subject for protocol violations. The IRB may also have to be contacted if safety to the subject or if the scientific soundness of the study is involved. All protocol deviations must be documented in the CRFs.

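### Subjects withdrawn because the ulcer deteriorated, and deaths, are censored in the primary time-to-heal analysis, which overstates healing and can bias the comparison in either direction if such losses differ by arm

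*Combined protocol and SAP*

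**What the plan says.** Section 6.4 (Subject Completion and Withdrawal) makes leaving the study, not only the treatment, compulsory: "subjects WILL be withdrawn from the study, in consultation with the Medical Monitor and the Investigator, if any of the following are met". Of the seven conditions listed, three describe worsening of the study ulcer: "A subject has a target ulcer wound bed that has exposed bone, tendon or fascia"; "Two separate infections with no response to allowable treatments"; and "The subject's ulcer merges with an adjacent ulcer". The other four are significant non-compliance, pregnancy, revascularization of the study leg, and an ulcer that cannot be dressed with compression. Section 13.3 adds a sponsor decision: "The Sponsor also has the right to discontinue the subject for protocol violations".

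On later data, section 6.4 says only: "Every attempt should be made to collect follow-up information". It sets no visits for this.

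Section 9.7 (Missing Data) gives the primary rule: "Missing primary endpoint data within 12 weeks from start of study will not be imputed for ITT populations as these will constitute right-censored data". The censoring time follows: "The last visit for which data are available will constitute the start of censoring (healing outcome". Death is listed there as a source of missing data, next to missed visits and loss to follow-up. No reason for withdrawal is treated differently, and there is no competing-event rule or sensitivity analysis for withdrawals. For secondary endpoints the same section uses last observation carried forward (LOCF) in the ITT population.

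Section 9.2 (H1) names the primary test: log-rank on a Kaplan-Meier analysis, 1A versus 2A at 6 weeks and 1A versus 2B at 12 weeks.

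**The concern.** Kaplan-Meier and log-rank are valid when a censored subject has the same future chance of healing as those still at risk. A subject removed because the ulcer merged with another, reached deep structures or stayed infected does not meet that condition, and neither does one who died. Sections 5.2 and 5.3 keep out ulcers that already reach muscle, tendon or bone and ulcers infected at S1 or TV1, so these triggers mark deterioration after entry.

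Removing such subjects takes failures out of the denominator, so the healing curve of any arm that loses them is too high. If the arms lose them at different rates, the primary test is shifted as well. Balance cannot be taken for granted in an open-label trial in which only one arm is grafted from TV1.

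The plan also treats the same subject in two ways. An ulcer still open at withdrawal counts as not healed in the proportion healed (LOCF), but as possibly healing later in the primary analysis.

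**Working it through.** **Inputs from the plan.** Section 9.3: 113 control and 112 graft subjects, two-sided 0.05, control healing 0.5 at 12 weeks, hazard ratio 1.74, dropout 0.033 per week (control) and 0.0083 per week (graft), power 86.1%. Section 5.1: 10% dropout expected in each arm.

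**The plan's own figure.** The control hazard is ln 2/12 = 0.0578 per week. Graft healing is 1 − 0.5^1.74 = 0.70. With the stated dropout, expected healings are 47.6 + 75.4 = 123. A Lakatos-type calculation gives 85.8% power (86.0% with one step per week). The Schoenfeld check is z = √(123 × 0.25) × ln 1.74 − 1.96 = 1.11, or 86.7%. The stated 86.1% is reproduced, so 50% and 70% are used as true healing below.

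**Assumption.** The documents give no rate of withdrawal for deterioration. Let f be the share of an arm so withdrawn, none of whom heal by week 12, with f from 2.5% to 10%. The top value would mean that all the dropout foreseen in section 5.1 is deterioration.

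**Effect on one arm, by hand.** Let P be true 12-week healing at a constant hazard, with all withdrawals at week 3. The unhealed share at week 3 is S = (1 − P)^(3/12). The estimate is 1 − S × (1 − P − f)/(S − f).

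- P = 50%, f = 10%: S = 0.841, and 1 − 0.841 × 0.400/0.741 = 54.6%.
- P = 70%, f = 10%: S = 0.740, and 1 − 0.740 × 0.200/0.640 = 76.9%.

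The ceiling, with every withdrawal before any healing, is P/(1 − f): 0.50/0.90 = 55.6% and 0.70/0.90 = 77.8%.

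**Other timings** (simulation, weekly visits; estimated 12-week healing):

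| f | True 50%: weeks 1-11 | weeks 1-8 | week 3 | True 70%: weeks 1-11 | weeks 1-8 | week 3 |
|---|---|---|---|---|---|---|
| 2.5% | 50.8 | about 51 | 51.0 | 71.0 | about 71 | 71.6 |
| 5% | 51.6 | 51.9 | 52.2 | 72.3 | 72.8 | 73.2 |
| 10% | 53.1 | 53.9 | 54.5 | 75.0 | 75.8 | 77.0 |

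Keeping the same subjects at risk as not healed to week 12 returns 50% and 70%.

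**Effect on the log-rank test.** Both arms truly heal 50%; 112 versus 113 subjects; 4,000 trials per setting for the rows at rates up to 10% (Monte Carlo standard error near 5% is √(0.05 × 0.95/4,000), about 0.3 points).

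| Withdrawn for deterioration, graft v control | False results at 12 weeks |
|---|---|
| 5% v 5%, 10% v 10% | 4.7-5.2% two-sided |
| 10% v 5% | 5.7-6.0% two-sided; about 4.5% on the graft side (weeks 1-8) |
| 10% v 0% | 6.7-9.6% two-sided, nearly all favouring graft |
| 0% v 10% | 7.4-9.2% two-sided, nearly all favouring control |
| 15% v 5% | 8.4% on the graft side |
| 5% v 15% | 8.1% on the control side |

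The nominal rate is 5% two-sided, 2.5% per side. With failures kept at risk, rejection stays near 5%.

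**Six weeks.** The effect is smaller. At 15% v 5%, false results on the graft side are 4.6% under the written rule and 3.2% with failures kept. At 10% v 5% no inflation is visible (two-sided 5.5% and 6.1%).

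**Limit of these runs.** They use whole arms. The planned 12-week comparison uses 2B, from which section 5.1 expects 30% of 2A to have moved to 2C.

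**The case against.** **The test may be unharmed.** A reader might infer that the rule inflates the primary result in favour of the graft. The documents do not support that. The primary result is a between-arm test, balanced losses leave its size intact, imbalance can favour either arm, and no rate by arm is given. The move from 2A to 2B at 12 weeks shifts the contrast for a separate reason, so the net direction is not fixed. This objection stands.

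**Large error rates need large losses.** The 15% rows exceed the 10% dropout in section 5.1 and only illustrate direction. At 10% versus 5% the effect is small. This also stands.

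**The null is a modelling choice.** Equal total healing with 15% v 5% failures requires non-failures to heal at 0.50/0.85 = 58.8% and 0.50/0.95 = 52.6%. If non-failures instead heal at the same rate in both arms, the written rule gives the graft no false win. It does move the hazard ratio from 0.86 to about 0.93, hiding part of a real graft disadvantage. The bias changes form but remains.

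**Follow-up could cure it.** Censoring is at the last visit with data. If an unhealed withdrawn subject were followed to TV13, censoring would fall at week 12, which is what the fix achieves. So the request for follow-up is not empty. The gap is that section 6.4 sets no visits and section 9.7 does not say that data after withdrawal are used.

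**Partial safeguards exist.** LOCF on the proportion healed, and withdrawals reported by group with reasons (section 9.7), would show some of the problem. But H2 compares 1A with 2B, is secondary, and does not correct the primary curve.

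**Counting triggers.** Inability to wear compression might be read as a fourth failure of the ulcer. It is not worsening as such and belongs in a sensitivity analysis.

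**Conclusion.** The primary analysis treats withdrawal for three kinds of ulcer deterioration, and death, as non-informative censoring, and that is not tenable. Under the assumed 2.5-10% per arm with withdrawals over weeks 1-8, 12-week healing is overstated by about 1-4 points at a true 50% and 1-6 points at a true 70%, or up to about 7 points if withdrawal comes earlier. This holds for each affected arm whether or not the arms are balanced.

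Bias in the log-rank test is conditional on imbalance. It leans toward the arm that loses more failures, is modest at 10% versus 5% (about 4.5% instead of 2.5% on that side), and is smaller at 6 weeks.

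The sizes rest on assumed rates and timing, and on withdrawn subjects not healing by week 12; some with infection might. This should be fixed before data are seen. Confidence is moderate, because the frequency of these withdrawals is unknown.

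**What to change.** 1. **SAP section 9.7, primary analysis.** Keep subjects withdrawn for any of the three deterioration reasons, and subjects who die, in the risk set as not healed to day 42 and day 84, unless closure is actually observed. Censor at the last visit for loss to follow-up or withdrawn consent.
2. **SAP section 9.7, sensitivity analysis.** Repeat the primary analysis counting every withdrawal as not healed, including inability to wear compression, non-compliance and protocol violation.
3. **Section 6.4.** Turn the general request for follow-up into recording closure status at TV7 and TV13, which are already scheduled, unless consent is withdrawn. State in section 9.7 that these data enter the primary analysis.

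The clinical withdrawal criteria and the care given are left as they are. The cost is some SAP wording, a paragraph in section 6.4, one extra analysis and a little more data collection. Reported healing rates may be slightly lower. Counting these subjects as not healed is a choice of estimand, so it should be stated as such.

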7 STANDARD OF CARE AND CONCOMITANT MEDICATIONS

Beginning at the S1 visit, ALL subjects must have their study ulcer managed using the SOC procedures noted below.

7.1 CLEANING THE STUDY ULCER

Remove the bandage and wash the leg. At any time when the bandage is removed, the leg should be elevated for as much time as possible.

Wash the leg with potable saline or tap water. Gently irrigate the study ulcer prior to each dressing change with warm tap water or saline. Strict aseptic technique is not needed.

During the Treatment Phase, the washing and cleaning of the VLU must be done with great care on the patients receiving epidermal grafting.

7.2 DEBRIDEMENT OF THE STUDY ULCER

It is important to remove all non-viable and necrotic material from the target ulcer prior to enrolling the patient. Extensive debridement is not permitted during the treatment phase. Care must be taken not to remove the graft by debriding the ulcer. Briefly, the following procedures should be followed,

1. The target ulcer and the surrounding skin are prepped with saline solution.
2. Anesthesia, topical or injected, is applied to the ulcer as necessary to reduce patient discomfort.
3. Using clean technique. All non-viable tissue in the wound bed is to be removed from the wound bed.
4. Ideally hemostasis is achieved using direct pressure. Cautery may be employed if necessary.

7.3 COMPRESSION BANDAGING

Multi-layer compression is applied at every visit following the manufacturer's suggested procedure technique. Patients cannot be enrolled until they have received at least 14 days of compression therapy. Training in compression wrapping will be provided.

7.4 SUBJECT INSTRUCTIONS

Subjects will be instructed to elevate the study ulcer limb above their heart as much as possible. Subjects will be instructed to keep the bandaging dry and to call or visit the study site if the bandaging becomes soiled or is removed.

7.5 CONCOMITANT MEDICATIONS

The subject may be administered any necessary medications, at the discretion of the Investigator, provided such medications are not applied topically to the ulcer surface (topical medication can be applied to other surfaces around the ulcer).

All medications and therapies administered or taken by the subject beginning 30 days prior to signing the ICF and throughout the study will be recorded in the source documents and, for randomized subjects, on the appropriate page of the Case Report Form (CRF).

7.5.1 EXCLUDED MEDICATIONS AND THERAPIES

The following treatments and medications are prohibited within 30 days prior to randomized treatment and throughout the study:

- Heat lamps
- UV lights
- Whirlpool baths
- Water Piks™
- Hyperbaric Oxygen
- Jet water streams (other than gentle saline irrigation)
- Wound dressings that include growth factors, engineered tissues or skin substitutes (e.g., Regranex®, Dermagraft®, Apligraf®, GraftJacket®, OASIS®, Primatrix®, Matristem®, etc.)
- Revascularization surgery on the leg with study (target) ulcer within 3 months
- Radiation therapy to the foot
- Topical antibiotics or other non-approved topical agents (with the exception of anesthetics used during debridement).
- Patients on Trental may remain on the medication but patients should not be started on Trental during the trial.
- Systemic steroids/oral corticosteroids (note: inhaled steroids are acceptable)
- Other Immunosuppressive agents
- Autoimmune disease therapies
- Cytostatic drugs
- Any investigational treatment/medications

7.5.2 ALLOWABLE MEDICATIONS AND THERAPIES

The following treatments are allowed during the study, if in the opinion of the Investigator, they are required for proper care of the research subject:

- Use of anesthetics for debridement.
- Treatment with systemic antibiotics for acute or chronic infection; however, prophylactic use of systemic antibiotics is not allowed.
- Topical antimicrobials as listed for use to treat an infection to the reference ulcer or at the scheduled treatment weeks.
- Use of Hibiclens Skin Cleanser for cleansing of general skin, wound and the harvest site. Alternatively, chlorhexidine soap may also be used.
- Other medications/therapies that are not otherwise prohibited and, in the opinion of the Investigator, are required for proper medical care.

8 DESCRIPTION OF PROTOCOL ASSESSMENTS AND PROCEDURES

8.1 INFORMED CONSENT

Written informed consent will be obtained for this study by the Investigator or suitably qualified designee from all subjects before the performance of any protocol-specific procedure. This study will be conducted in accordance with the provisions of the Declaration of Helsinki.

In obtaining and documenting informed consent the Investigator must comply with applicable regulatory requirements and must adhere to Good Clinical Practice (GCP). Evidence of GCP training is required for all investigators. The Investigator, or designee, must fully inform subjects of all pertinent aspects of the study. Before informed consent may be obtained, the Investigator, or a person designated by the Investigator, must provide the subject ample time and opportunity to inquire about details of the study and to decide whether or not to participate in the trial. All questions about the trial must be answered to the satisfaction of the subject. Prior to the subject's participation in the trial, the written informed consent must be signed and personally dated by the subject and by the person who conducted the informed consent discussion.

8.2 ASSESSMENT OF ELIGIBILITY

At each visit during the Screening Period, the Investigator must assess a subject's continued suitability and eligibility for the trial, especially with regards to the Inclusion and Exclusion criteria. If the subject is not suitable or eligible for the trial, then the subject will be a screen failure. Screen failure subjects may be re-entered into the study at a later time and re-screened.

8.4 SUBJECT DEMOGRAPHICS, MEDICAL HISTORY, ULCER HISTORY

8.4.1 DEMOGRAPHICS

For the purposes of this study, demographic information will include:

- Dates of Informed Consent Form signature
- Date of birth
- Gender
- Race (American Indian/Alaskan Native, Asian, Black/African American, Native Hawaiian/Pacific Islander, Caucasian, or other)
- Ethnicity (Hispanic/Latino or Not Hispanic/Latino)
- Use of tobacco products

8.4.2 MEDICAL HISTORY

A medical history will be recorded during the Screening Period and will include:

- ALL ongoing medical conditions
- ALL previously resolved medical conditions related to Venous Insufficiency or Leg Ulceration or which are relevant in the opinion of the Investigator
- ANY prior medical conditions that have resolved within the last year

Events that emerge prior to the randomization visit (TV1) will be recorded in the medical history and not as Adverse Events. Aside from being used to determine subject eligibility, this information will permit the Investigator to record the nature, duration and severity of any ongoing baseline medical conditions prior to receiving investigational product treatment.

Medical histories will be recorded using the body system categories outlined below:

- Cardiovascular
- Respiratory
- Gastrointestinal
- Renal
- Hepatic
- Lymphatic
- Hematologic
- Immunologic
- Dermatologic
- Psychiatric

CELLUTOME™ IN VENOUS LEG

- Neurological
- Endocrine
- Genitourinary
- Other

For each relevant history, the following will be documented:

- Disease/disorder/condition
- Date of diagnosis
- History status (resolved or ongoing)

8.4.3 LEG ULCER HISTORY

- Duration of the current VLU

Note: 'Duration' is defined as the length of time that the study ulcer has been open at this location since the last time it was fully closed.

- Current bandaging system used for the VLU and length of time that this has been used
- Prior treatments that have been used on the VLU
- Age when the subject developed his/her first VLU
- Total number of previous VLUs
- Location of the current VLU

Note: 'Study ulcer location' is defined by the ulcer being on the left or right leg, by the location of the ulcer on the malleolus, low gaiter or high calf, and by the positioning of the ulcer as lateral, medial, anterior or posterior.

- Number of additional VLUs and location of each present at the screening visits
- History of VLU recurrence

Note: 'Recurrence' is defined as the re-opening of the study ulcer after complete healing.

- History of a DVT (deep vein thrombosis) in the study leg
- Presence of hyper-pigmentation, edema, varicosities, lipodermatosclerosis, thickened nails and dermatitis.

